## Statistical Analysis Plan

Sponsor: Zogenix International Limited; Protocol No.: ZX008 Study 2 (ZX008-1501 and ZX008-1502)

---

completed items in a scale. The scaled results will be combined across age categories to produce a single score for each functional area.

A Psychosocial Health Summary score is computed as the sum of the items over the number of items answered in the Emotional, Social, and School Functioning Scales.

A Physical Health Summary score is made up of the Physical Functioning Scale Score.

The Total Score is computed as the sum of all the items over the number of items answered on all the Scales.

Descriptive statistics at both Baseline and EOS/ET will be provided for the Psychosocial Health Summary score, the Physical Health Summary score and Total Score.

The change from baseline for the Total Score will be calculated for each subject by subtracting the Total Score measured at Baseline from the Total Score measured at End of Study/ET. The change from baseline will be summarized with descriptive statistics and treatment groups will be compared on the Total Score using pairwise Wilcoxon tests.

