### 2.2. Secondary Objective(s)

The key secondary objectives of Study 2 are:

- To demonstrate that ZX008 0.2 mg/kg/day is superior to placebo as adjunctive therapy in the treatment of Dravet syndrome based on change in the frequency of convulsive seizures between baseline and T+M.
- To demonstrate that the ZX008 0.2 and 0.8 mg/kg/day dose groups are (independently) superior to placebo on the following endpoints:
  - The proportion of subjects who achieve a  $\geq 50\%$  reduction from baseline in convulsive seizure frequency.
  - The longest convulsive seizure-free interval.

Additional Secondary Objectives:

- To demonstrate that the ZX008 0.2 and 0.8 mg/kg/day dose groups are (independently) superior to placebo on the following endpoints:
  - The number of convulsive seizure-free days.
  - The proportion of subjects who achieve  $\geq 25\%$ , or  $\geq 75\%$ , or 100%, or near seizure-free (ie, at most 1 convulsive seizure) reductions from baseline in convulsive seizure frequency.
  - The change from baseline in non-convulsive seizure frequency.
  - The change from baseline in convulsive + non-convulsive seizure frequency
  - The incidence of rescue medication usage
  - The incidence of hospitalization to treat seizures
  - The incidence of status epilepticus.
- To demonstrate that the ZX008 0.2 and 0.8 mg/kg/day dose groups are (independently) superior to placebo on the following endpoints:
  - Clinical Global Impression – Improvement rating, as assessed by the principal investigator.
  - Clinical Global Impression – Improvement rating, as assessed by the parent/caregiver.
  - The change from baseline in the Quality of Life in Childhood Epilepsy (QOLCE) score.
  - The change from baseline in the Pediatric Quality of Life Inventory™ (PedsQL) score.
  - The change from baseline in the PedsQL Family Impact module score.
  - The change from baseline in the QoL of the parent/caregiver using the EQ-5D-5L scale.
  - The change from baseline in the affective symptoms of the parent/caregiver using the Hospital Anxiety and Depression Scale (HADS).

The safety objective of the Study 2 is:

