### 2.6. Treatment Assignment & Blinding

Subjects in Study 2 were originally in either Study 1501 or Study 1502. Upon completion of the Baseline Period, subjects who qualify for the study will be randomized (1:1:1) in a double-blind manner to receive 1 of 2 doses of ZX008 (0.2 mg/kg/day, 0.8 mg/kg/day; 30mg/day maximum) or placebo. The randomization was stratified by age (<6 years,  $\geq 6$  years) to ensure balance across treatment arms, with

This document is confidential.

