**Statistical Analysis Plan**

Sponsor: Zogenix International Limited; Protocol No.: ZX008 Study 2 (ZX008-1501 and ZX008-1502)

Section 6: Social Activities	Stigma Item	6.1 i
Section 7: Behavior	Behavior	7.1 a, c, f, g, h, i, j, k, l, m, o, q, r, s, t
Section 8: General Health	General Health Item	8.1
Section 2 (USA Version) or Section 9 (Australia Version)	Quality of Life Item	2.1 or 9.1
Overall Quality of Life *		Average of 16 subscale scores*

\*An Overall Quality of Life Score can be computed by adding each subscale score for each individual and then dividing by 16.

For each treatment group at Baseline and End of Study/ET, the mean (SD) score will be presented for each QOLCE subscale and for the overall quality of life score.

In addition, the change from baseline in the overall QOLCE will be calculated for each subject by subtracting the baseline overall score from the overall score measured at End of Study/ET. The change from baseline for each treatment group will be summarized by the mean (SD) and treatment groups will be compared using pairwise Wilcoxon tests.

Individual subject data for the domains will be listed.

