**Quality of Life of the Parent/Caregiver using EQ-5D-5L Scale**

The impact on the quality of life of the parent/caregiver responsible for a patient with DS will be assessed at Baseline (Visit 3) and at End of study (Visit 12) using the EQ-5D-5L. The responsible parent/caregiver was permitted to opt out of completing the EQ-5D-5L.

The EQ-5D-5L health questionnaire is a health-related quality of life instrument with 5 dimensions: mobility, self-care, usual activities, pain/discomfort, and anxiety/depression. Each dimension has 5 possible levels: no problems, slight problems, moderate problems, severe problems and extreme problems.

The summary of results will follow the EQ-5D-5L guideline results presentation. For the "Health Profiles" descriptive system summary results will show the number, and proportion (%) of subjects in each Item score (No Problems, Slight Problems, Moderate Problem, Severe Problem, Extreme Problems) by treatment at baseline and at the end of study. In addition, the item scores will be classified into two categories as "No Problems" and "Problems," the latter comprised of slight, moderate, severe and extreme problems. Summary results will show number of patients and proportion (%) with "No Problems" and with "Problems" by treatment at baseline and at end of study.

For the VAS measure of overall self-rated health status, descriptive statistics summary results will be presented for the VAS score showing number of subjects, mean, standard deviation, median, and range by each treatment at baseline and end of study time points.

The change from baseline in VAS will be calculated by subtracting the VAS score at baseline from the VAS score obtained at End of Study/ET. The change in VAS will be summarized using descriptive statistics, and treatment groups will be compared using pairwise Wilcoxon tests.

The quality of life of parent/caregiver individual data will be listed using EQ-5D-5L scale.

This document is confidential.

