### Parent/Caregiver Assessment using HADS Scale

The HADS is a tool commonly used to determine the levels of anxiety and depression that a person is experiencing and is administered to the primary parent/caregiver to assess these symptoms longitudinally during the study. The responsible parent/caregiver was permitted to opt out of the HADS. The HADS is a 14-item scale that generates ordinal data for two dimensions: 1) Anxiety and 2) Depression. Seven of the items relate to anxiety and 7 relate to depression.

Each item has 4 possible answers rated 0-3. All answers to the items for a dimension with their respective rating are added resulting in a range for each dimension from 0-21. Scores for the entire scale (emotional distress) range from 0 to 42, with higher scores indicating more distress.

Summary descriptive statistics including the mean and SD will be generated separately for the Anxiety and Depression dimensions at both Baseline and at End of Study/ET. In addition, each subject will be categorized at each time point based on the score cut-offs below which were validated on adult patients in a treatment setting.

Score	Category
0-7	Normal
8-10	Borderline abnormal
11-21	Abnormal

Summary statistics will include number and proportion (%) of subjects in each of the categories above at each study visit.

In addition, the total score for Anxiety and Depression will be generated. Descriptive statistics summaries including mean, median, standard deviation, median and range will be summarized for each treatment at Baseline and End of Study/ET.

The change from baseline for each subject will be calculated by subtracting the total Anxiety and Depression score measured at Baseline from the analogous score measured at End of Study/ET. The change from baseline will be summarized by descriptive statistics and the difference between treatment groups will be assessed using pairwise Wilcoxon tests.

The individual item outcomes will be presented in the subject data listing.

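### QOLCE, PedsQL, EQ-5D VAS and HADS are tested by Wilcoxon on change, with no baseline covariate and no age stratum: valid, but precision is given up

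*SAP*

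**What the plan says.** Section 2.2 of the Study 2 SAP lists these scales among the additional secondary objectives, under the aim "To demonstrate that the ZX008 0.2 and 0.8 mg/kg/day dose groups are (independently) superior to placebo on the following endpoints". They are therefore inferential comparisons, but section 6.3 leaves them out of the six formally ordered tests.

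Section 8.2.2 sets the tests:

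- **Overall QOLCE:** the change is "summarized by the mean (SD) and treatment groups will be compared using pairwise Wilcoxon tests".
- **EQ-5D VAS:** the change is "summarized using descriptive statistics, and treatment groups will be compared using pairwise Wilcoxon tests".
- **HADS total:** "the difference between treatment groups will be assessed using pairwise Wilcoxon tests".
- **PedsQL Total:** the change is obtained by "subtracting the Total Score measured at Baseline from the Total Score measured at End of Study/ET", and then "treatment groups will be compared on the Total Score using pairwise Wilcoxon tests". That sentence names the Total Score, but the text around it concerns the change in that score.

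None of the four sections names a baseline covariate, an age term or a between-group estimate. Sections 6.3.3.11 to 6.3.3.14 of the Study 1 SAP specify the same tests. All four instruments are collected at Visit 3 (section 2.8, Table 4). Section 2.6 states: "The randomization was stratified by age (<6 years" against 6 years and over).

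**The concern.** The baseline score and the age stratum are both in hand, and the SAP uses one or both in most of its other comparisons with placebo. For these four scales it does not, and it gives no reason. Subtracting baseline fixes its coefficient at 1. When the true regression slope of end score on baseline is below 1, subtraction over-corrects and leaves regression to the mean in the error term. Omitting the stratum costs a little more if age predicts the change.

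At stake is the sensitivity of the plan's comparisons on child and caregiver quality of life, in a rare disease where the SAP itself cites slow enrolment.

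**Working it through.** **The plan's own power figure.** Section 2.5 of the Study 2 SAP gives 40 per arm, 90% power, a 40-point difference and SD 55, two-sided 0.05. By the normal formula, n = 2 × (1.960 + 1.282)² × (55/40)² = 39.7, so 40 per arm, with power 0.902 (t-based 0.895). It reproduces. It concerns the primary endpoint; the SAP gives no power, SD or ρ for the four scales.

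**What the SAP does elsewhere (sections 8.1 to 8.2.2).**

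| Endpoint | Baseline term | Age term |
|---|---|---|
| Primary ANCOVA | yes | yes |
| Seizure-free days | yes | follows the primary approach |
| Non-convulsive and total seizures (rank ANCOVA) | yes | none named |
| Rescue medication days (rank ANCOVA) | yes | none named |
| Status epilepticus (logistic) | yes | yes |
| Responders (logistic) | response is relative to baseline | yes |
| Hospitalization, CGI-I (CMH) | no | yes |
| Longest interval (Wilcoxon) | no | no |
| The four scales (Wilcoxon on change) | subtraction only | no |

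**Variance comparison.** Let σb and σe be the baseline and end SDs and ρ their within-arm correlation.

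- Change score: σe² + σb² − 2ρσeσb
- Baseline-adjusted: σe²(1 − ρ²)
- Difference: (σb − ρσe)², which is never negative and is zero only when the slope ρσe/σb equals 1.

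With equal SDs the two become 2σ²(1 − ρ) and σ²(1 − ρ²), a ratio of (1 + ρ)/2. The power column assumes that the change-score test has 80% power, and equals Φ[(1.960 + 0.842)/√ratio − 1.960].

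| ρ (assumed) | Variance ratio | SE reduction | Per arm needed unadjusted to match adjusted 40 | Power, from 80% |
|---|---|---|---|---|
| 0.3 | 0.65 | 19.4% | 61.5 | 93.5% |
| 0.5 | 0.75 | 13.4% | 53.3 | 89.9% |
| 0.7 | 0.85 | 7.8% | 47.1 | 86.0% |
| 0.8 | 0.90 | 5.1% | 44.4 | 84.0% |
| 0.9 | 0.95 | 2.5% | 42.1 | 82.0% |

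**Check on ranks.** The formula is for means, so rank tests were simulated: 40 per arm, scores rounded to whole numbers, 25% aged under 6, 4000 runs. The Monte Carlo SE at power 0.78 is √(0.78 × 0.22/4000) = 0.0065. The age effect is an assumed shift of 0 or 0.5 SD.

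| ρ | Age effect | Wilcoxon on change | End-score ranks + baseline ranks | Change ranks + baseline ranks + age |
|---|---|---|---|---|
| 0.3 | 0 | 0.777 | 0.918 | 0.910 |
| 0.5 | 0 | 0.769 | 0.864 | 0.871 |
| 0.7 | 0 | 0.767 | 0.808 | 0.828 |
| 0.8 | 0 | 0.778 | 0.789 | 0.819 |
| 0.3 | 0.5 | 0.762 | 0.916 | 0.911 |
| 0.5 | 0.5 | 0.737 | 0.840 | 0.855 |
| 0.7 | 0.5 | 0.750 | 0.782 | 0.828 |
| 0.8 | 0.5 | 0.740 | 0.740 | 0.810 |

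Under the null, rejection rates lay between 0.040 and 0.060 for all three methods. At ρ 0.8 the end-score rank model without age gains almost nothing, and nothing at all when age is prognostic. End-score ranks with both baseline ranks and age were not simulated.

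**The case against.** The strongest reply is that nothing here is an error. A Wilcoxon test on change is valid under randomisation, and these endpoints are outside the hierarchy. That stands, and it limits the point to an efficiency gain.

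Several narrower objections also stand:

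- A reader might infer that the tests ignore baseline. They do not: every section subtracts it. What is missing is its use as a covariate.
- A reader might infer that the SAP adjusts everywhere else. It does not. Longest interval, a key secondary endpoint, is also an unadjusted Wilcoxon, and the rank ANCOVA text names no age factor.
- Over-correction is not automatic at every ρ below 1. It depends on the slope, and the (1+ρ)/2 ratio needs equal SDs.
- At ρ of 0.8 to 0.9 the gain is small.
- The age argument is uneven. EQ-5D VAS and HADS describe the caregiver, and nothing in the SAP shows that the child's age predicts their change. The cut at 6 years runs through the PedsQL form for ages 5 to 7, so an age term does not resolve the pooling of forms.
- Caregivers could opt out of EQ-5D-5L and HADS, so fewer than 40 per arm may contribute. The variance ratio does not depend on n, but the subject counts and powers above do.
- Study 1 was reported in September 2017 with the same tests, so replacing them outright in Study 2 would lose like-for-like comparison.

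These narrow the point but do not remove it: the baseline data are already collected, and the model needs only a small extension of one that the SAP contains.

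**Conclusion.** The point holds as a minor, optional improvement. For the four scales the SAP uses baseline only by subtraction and omits the randomisation stratum, so it gives up precision that most of its other secondary analyses recover.

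Under equal SDs the loss is an SE inflation that adjustment would reduce by about 19% at ρ 0.3 and 2.5% at ρ 0.9. At 40 per arm, over ρ 0.3 to 0.8, that is worth about 22 down to 4 subjects per arm. Both ρ and the 80% reference power are assumptions. In the rank simulation the gain shrank as ρ rose, and at ρ 0.7 to 0.8 it depended on which rank model was used.

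The documents do not support a reading of bias, inflated type I error or damage to the efficacy conclusions. Chance baseline imbalance left in the comparison is random error, and the primary and key secondary tests do not involve these scales.

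**What to change.** In section 8.2.2 of the Study 2 SAP, for overall QOLCE, EQ-5D VAS, HADS total and PedsQL Total:

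1. Make the comparison of each dose with placebo a rank ANCOVA: ranks of the End of Study/ET score as response, ranks of the baseline score as covariate, treatment as factor. This extends the SAP's existing rank ANCOVA by adding age group (<6, ≥6 years) as a factor, which should be stated explicitly.
2. Report the adjusted difference in scale points with its 95% CI from a separate ordinary ANCOVA on the score with the same terms. A model on ranks cannot supply a difference in scale points.
3. Keep the pairwise Wilcoxon on change as supportive, so that Study 2 can be set beside the reported Study 1 results.

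The cost is SAP wording, minor extra programming and one more reported analysis per scale. No new data are needed. The change should be fixed before Study 2 is unblinded.

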### **Pediatric Quality of Life Inventory (PedsQL 2.0 Family Impact Module) Scale**

The PedsQL™ Family Impact Module was designed to measure the impact of pediatric chronic health conditions on parents and the family. The PedsQL™ Family Impact Module measures parent self-reported physical, emotional, social, and cognitive functioning, communication, and worry. The Module also measures parent-reported family daily activities and family relationships.

There are 6 items for Physical Functioning, 5 items each for Emotional Functioning, Cognitive Functioning and Worry, 4 for Social Functioning, and 3 for Communication. There are additionally 3 questions for Daily Activities and 5 for Family Relationships.

Each of the responses to the 36 items is initially scored on a 5 point Likert scale from 0 (Never) to 4 (Almost always). Scores will be linearly transformed to a scale of 0 to 100, where 0=100, 1=75, 2=50, 3=25 and 4=0, and higher scores mean better health related quality of life. If more than 50% of the items in the scale are missing, the scale scores should not be computed. A mean score is calculated as the sum of the items over the number of items answered. If some of the answers on a scale are missing but 50% or more of the items in the scale are completed, then impute the mean of the completed items in a scale.

The Parent HRQL Summary Score (20 items) is computed as the sum of the items divided by the number of items answered in the Physical, Emotional, Social, and Cognitive Functioning scales.

The Family Functioning Summary Score (8 items) is computed as the sum of the items divided by the number of items answered in the Daily Activities and Family Relationships scales.

The Total Score is the sum of all 36 items divided by the number of items answered.

Descriptive statistics for baseline and EOS/ET will be provided for the summary scores.

This document is confidential.

**Statistical Analysis Plan**

Sponsor: Zogenix International Limited; Protocol No.: ZX008 Study 2 (ZX008-1501 and ZX008-1502)

---

8.2.3. Exploratory Analyses

Exploratory analysis may be performed by comparing of ZX008 0.2 and 0.8 mg/kg/day doses on primary, secondary, safety and PK endpoints.

Thus, all comparisons planned for ZX008 to placebo may be repeated to compare the ZX008 0.2 and 0.8 mg/kg/day doses.

Additional exploratory analyses may include descriptive summaries of the primary endpoint by:

- SCN1a Mutation Status
- seizure type
- baseline seizure frequency
- Age (greater than or equal to 13 years at baseline)
- Concomitant AED: VPA, CLB, VPA+CLB
- Number of concomitant AEDs

This document cannot be used to support any marketing authorization application and any extensions or variations thereof.

PUBLIC COPY

This document is confidential.

## 9. Analysis Of Pharmacokinetics

The bioanalytical methods for the determination of individual plasma concentrations of fenfluramine and its metabolite (norfenfluramine) will be reported together with the plasma concentration results in separate bioanalytical reports. These bioanalytical reports will be issued as a separate report.

This document cannot be used to support any marketing authorization application and any extensions or variations thereof.

PUBLIC COPY

This document is confidential.

## 10. Safety

All safety analyses will be performed for the Safety population (SAF) and will be reported by treatment group as well as ZX008 combined for the 16-week treatment period unless noted otherwise.

### 10.1. Extent of Exposure

Treatment exposure data will be summarized and analyzed for the SAF population.

Duration of total exposure to ZX008 (i.e., time on treatment (in days)) will be calculated per subject as the number of days with IMP intake during the trial, and will be summarized using n, mean, standard error, median, minimum, Q1, Q3 and maximum.

This will be calculated as:

Date of last IMP intake – Date of first IMP intake + 1

Time on treatment will be summarized by treatment group.

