**Taper Period:**

Subjects who complete the Maintenance Period and were not continuing into the open-label extension study and subjects who discontinued from the study early were to be tapered off from study medication. Study medication was administered as equal doses BID in the morning and in the evening approximately 12 hours apart, with food. Each dose should have been separated by a minimum of 8 hours and a maximum of 12 hours. A missed dose of study medication may have been taken later up to 8 hours before the next scheduled dose; otherwise, the missed dose should not be given. IMP was administered using the oral dosing syringe provided.

In order to maintain the blind across all dose groups, all subjects who did not continue into the open-extension study participated in a dose-tapering procedure over the course of 8 days. On the first day of the tapering period subjects in the ZX008 0.8 mg/kg/day group decreased to a dose of ZX008 0.4 mg/kg/day BID (maximum 30mg/day). After 4 days at this dose level (Day 5), subjects randomized to the ZX008 0.8 mg/kg/day group decreased their dose to 0.2 mg/kg/day. Subjects in the ZX008 0.2 mg/kg/day group decreased their dose to placebo on the first day of tapering while doses in the placebo group remained constant throughout the tapering procedure. On Day 9, all subjects stopped taking study medication. The taper was expected to take a total of 8 days (Table 2). A new bottle of IMP was started by the subject at each level of the taper step.

Table 2. Taper Algorithm

Randomized Group	Taper Step 1 Day 1-4 after study completion or early termination	Taper Step 2 Days 5-8 after study completion or early termination

This document is confidential.

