### 5.2. Safety (SAF) Population

All safety analyses will be performed on the SAF Population defined as all randomized subjects who receive at least one dose of ZX008 or placebo. Subjects will be analyzed according to the treatment group to which they were randomized.

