### 10.2. Treatment Compliance

Study medication is to be administered twice daily, and compliance is recorded in the eDiary as full (both doses), partial (less than full daily dose) or missed (both doses) each day. From this, compliance will be calculated by assuming that a missed dose=0% of dose consumed, partial=50% of dose consumed, and full=100% of dose consumed. For each subject, a daily compliance score will be thus obtained.

Compliance will be summarized for the SAF and mITT populations over the course of T+M and Maintenance only, reported by treatment group.

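### Exposure to ZX008 is defined as days with intake but computed as the first-to-last span of all IMP, so ZX008 days are miscounted for 0.2 mg/kg/day subjects who taper and placebo subjects who enter the extension

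*SAP*

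**What the plan says.** Study 2 SAP, Section 10.1, names the variable duration of total exposure to ZX008, glosses it as time on treatment in days, and states that it "will be calculated per subject as the number of days with IMP intake during the trial". The formula directly below is "Date of last IMP intake – Date of first IMP intake + 1". The same section adds: "Time on treatment will be summarized by treatment group". Section 6.2.4.1 of the Study 1 SAP has the same definition and formula, with fenfluramine hydrochloride as the named drug.

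Four other places in the Study 2 SAP determine what this variable will contain:

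- **Section 10.2:** "compliance is recorded in the eDiary as full (both doses), partial (less than full daily dose) or missed (both doses) each day". Wholly missed days are therefore foreseen and recorded.
- **Section 2.7, Taper Period and Table 2:** "Subjects in the ZX008 0.2 mg/kg/day group decreased their dose to placebo on the first day of tapering". The taper lasts 8 days, and its bottles are called IMP.
- **Section 2.7, Transition Period and Table 3:** subjects randomized to placebo who enter the extension take ZX008 0.2 mg/kg/day from the first transition day, for two weeks. These bottles are also called IMP.
- **Section 5.2:** "Subjects will be analyzed according to the treatment group to which they were randomized".

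Section 10 sets a 16-week window for safety reporting, which includes the taper/transition weeks. Nothing in Section 10.1 stops the count at Visit 12, removes missed days, or separates placebo days from ZX008 days.

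**The concern.** There are two separate faults.

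The first is between definition and formula. A count of days with intake and a calendar span are different quantities, and a programmer who follows the formula will not produce what the sentence defines.

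The second is between label and content. The variable is called exposure to ZX008 but counts IMP, and the product inside the IMP bottle changes after Visit 12 in two arms. This fault lies in the wording as well as the formula, so correcting the formula alone would leave it in place.

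At stake is Table 14.1.5.1, which readers will use to judge how much drug each arm received when they look at safety. Treatment-emergent events are presented by assigned group through Visit 13. The schedule of assessments allows the Visit 12 echocardiogram up to Day 113, so a placebo subject could be imaged after as many as 14 days on ZX008 (Day 99 to Day 113). The exposure table is the natural place to show that, and as specified it cannot.

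**Working it through.** **Inputs (Study 2 SAP).** T+M is 98 days (Section 6.4). The taper is 8 days and the transition two weeks, 14 days (Section 2.7). The double-blind period is 2 + 12 + 2 weeks (Section 6.5). The treatment-completer threshold is compliance on at least 85% of dosing days (Section 6.2). The number of subjects who taper or transition, and the share of wholly missed days, are not given.

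**The plan's own period.** 14 + 84 + 14 = 112 days = 16 weeks, as stated.

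**Formula against ZX008 days, with no missed days.**

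| Subject | Last − first + 1 | Days on ZX008 | Difference |
|---|---|---|---|
| 0.2 mg/kg/day, tapers | 98 + 8 = 106 | 98 | 8 placebo days; 8/98 = +8.2% |
| 0.2 mg/kg/day, enters extension | 98 + 14 = 112 | 112 | none |
| 0.8 mg/kg/day, tapers | 98 + 8 = 106 | 106 | none; this arm tapers on active drug |
| 0.8 mg/kg/day, enters extension | 98 + 14 = 112 | 112 | none |
| Placebo, enters extension | 98 + 14 = 112 | 14 | 14/112 = 12.5% of the days in the placebo column are ZX008 |
| Placebo, tapers | 98 + 8 = 106 | 0 | all placebo, under a ZX008 label |

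Counting T+M to Visit 12 at Day 99 gives 107 against 99 in the first row and 113 for a placebo subject who transitions. The 8 and 14 misassigned days do not change.

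**Early stop.** A 0.2 mg/kg/day subject who stops at Day 14 and then tapers gets 14 + 8 = 22 days against 14 on ZX008: 8/14 = +57%.

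**Missed days (assumption).** The formula counts every wholly missed day between first and last intake. For a subject exactly at the 85% threshold, up to 15% of 98 = 14.7 T+M days could be wholly missed. The number could also be zero, because the shortfall may consist of partial days, and a partial day has intake. The range is therefore 0 to about 15 days. For a 0.2 mg/kg/day subject who tapers, ZX008 days then run from 98 down to 98 − 14.7 = 83.3, and the overstatement from 106/98 − 1 = 8.2% to 106/83.3 − 1 = 27.3%.

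**The case against.** The best defence is that this is one descriptive table. Section 10.3 takes adverse event percentages over the number of subjects in the safety population, the cardiovascular SAPs use subject counts and mean changes, and no person-time rate is planned anywhere. All of that stands. A reader might infer that exposure is the denominator for the safety results; the documents do not support that.

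A reader might also infer that the formula fails in every arm. It does not: for adherent subjects in the 0.8 mg/kg/day arm, and for adherent 0.2 mg/kg/day subjects who enter the extension, it gives the right ZX008 count. Nor are placebo subjects' transition days reported as no exposure. They are counted, but in the placebo column. Analysing safety as randomized is itself a declared choice (Section 12), and the transition dosing is set out in Section 2.7. The 85% threshold does not imply 15 days without drug. It is a floor for completers, and 15 is the upper end of a range that starts at zero.

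It can further be said that a calendar span is a conventional measure of time on treatment, that missed doses are covered by the compliance summary and Listings 16.2.5.1 to 16.2.5.3, and that half-lives of about 20 and 30 hours (cardiovascular SAP, Section 1) mean one missed day is not a drug-free day. These points support keeping the span under a different name. They do not make it a count of days with intake, and none of them addresses placebo taken in the taper or ZX008 taken by placebo subjects in the transition.

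**Conclusion.** The point holds in limited form. In both SAPs the definition and the formula disagree, and the ZX008 label does not match a count of IMP. Followed as written, the rule adds 8 placebo days for each 0.2 mg/kg/day subject who completes the full taper (+8.2% on a 98-day T+M, more after an early stop). It also leaves 14 ZX008 days visible only in the placebo column for each placebo subject who completes the transition. No other section corrects this.

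These per-subject figures rest on the planned period lengths. The effect on an arm mean cannot be computed, because the numbers who taper or transition are not stated. The missed-day component is an assumption, 0 to about 15 T+M days for a subject at the 85% threshold. The consequence is confined to Table 14.1.5.1 and to how safety is read against it. Adverse event percentages, cardiac counts and efficacy tests do not change. It should be corrected because the remedy is small and uses data already collected.

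**What to change.** In Section 10.1 of the Study 2 SAP, with the same change to Section 6.2.4.1 of the Study 1 SAP or a note in its report:

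1. Keep last minus first plus 1, but rename it *time on IMP (including taper/transition)*.
2. Report T+M duration, and the number of T+M days with full or partial intake from the eDiary record that supports Section 10.2 and Listing 16.2.5.1.
3. State a rule for days with no eDiary entry. Treating them as no intake could understate exposure in a safety table. One option is to show them as a separate count and give exposure with and without them.
4. Report taper and transition days separately, by the product actually taken. Placebo taper days in the 0.2 mg/kg/day arm then no longer count as ZX008, and ZX008 transition days in the placebo arm are shown as such.

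The cost is one extra derivation and a few more rows in Table 14.1.5.1. Stated ZX008 exposure will be slightly shorter. No dose, schedule or other analysis is touched.
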